2.1. Study design and participants

This prospective observational study was conducted at the Department of Periodontology, Faculty of Dentistry, Istanbul Medipol University. The study was approved by the ethics committee of Istanbul Medipol University in accordance with the Declaration of Helsinki (World Medical Association, 2013) (Decision No: 1553; Date: 11 December 2025). The study was reported in accordance with the Strengthening the Reporting of Observational Studies in Epidemiology (STROBE) statement (von Elm et al., 2007). Written informed consent was obtained from all participants before enrollment, and participation was voluntary without any effect on periodontal treatment.

Sample size estimation was based on the 3-month deep-pocket PPD difference reported by Teughels et al. (2013) (SRP + probiotic: 2.88 ± 0.35 mm; SRP + placebo: 2.25 ± 0.27 mm). Using a conservative standardized effect size of 0.50, a two-sided α of 0.05 and 80% power, at least 63 patients per group were required; therefore, 65 patients were included in each group. Because the present study was observational and exposure was not investigator-assigned, this calculation was used to estimate an adequate minimum group size for detecting clinically relevant between-group differences rather than to support causal inference.

Patients scheduled to undergo NSPT were consecutively screened for eligibility at the periodontal clinic. Of 184 patients screened, 140 eligible patients were enrolled after pre-enrollment exclusions, and 130 patients who completed the required follow-up assessments were included in the final analysis. Eligible participants were 18–70 years of age, had at least 20 natural teeth, were diagnosed with Stage III Grade B periodontitis and were available for baseline, 1-month and 3-month evaluations. Patients were excluded if they had used systemic antibiotics within the previous 3 months, had received periodontal treatment within the previous 6 months, had systemic disease, were pregnant or lactating, or had severe cognitive or psychiatric conditions that could interfere with questionnaire completion or follow-up. Current smoking status was recorded at baseline and was not used as an exclusion criterion.

The final analytic sample comprised 65 patients in the probiotic product-use group and 65 patients in the non-user group.

2.2. Periodontal diagnosis, treatment and probiotic exposure definition

Periodontal diagnosis and stage/grade assignment were established according to the 2017 World Workshop classification of periodontal diseases and conditions (Papapanou et al., 2018; Tonetti et al., 2018). Only patients with Stage III Grade B periodontitis were included. Periodontitis was defined by detectable interdental CAL at two or more non-adjacent teeth. Stage III Grade B periodontitis was defined by interdental CAL ≥ 5 mm at the site of greatest loss, with grading based on a bone loss/age ratio of 0.25–1.00.

All patients received routine NSPT, including individualized oral hygiene instruction and supra- and subgingival mechanical debridement/root surface instrumentation where indicated (Herrera et al., 2020; Suvan et al., 2020). All NSPT procedures were performed by the same periodontist ([name]).

The study did not include an investigator-assigned probiotic intervention. No probiotic strain, dose, formulation, frequency, duration or adherence protocol was prescribed as part of the study. Group classification was based on self-reported use of probiotic supplements or commercially labelled probiotic products during active periodontal treatment and post-treatment follow-up. Patients who reported such use were classified as probiotic product users, whereas those reporting no probiotic supplement or commercially labelled probiotic product use during the same interval were classified as non-users. Traditional homemade fermented foods, including homemade yogurt, kefir, pickles, vinegar, sourdough products and boza, were recorded as dietary fermented-food habits when reported but were not used to define probiotic exposure because strain composition, colony-forming unit content, microbial viability, dose and consistency of intake could not be verified (FAO/WHO, 2002; Hill et al., 2014; Sahin, 2026). Therefore, the exposure represented self-reported real-world probiotic-labelled product use rather than standardized probiotic intake.

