2.3. Clinical assessment

Clinical periodontal measurements including PI, BOP, PPD, CAL were performed at baseline, 1 month, and 3 months after NSPT by a calibrated examiner ([name]) who was not involved in treatment delivery and was blinded to participants' probiotic product-use status and questionnaire responses. Participants were instructed not to disclose their probiotic product use during clinical examinations. Probiotic product-use data and questionnaire responses were recorded separately from the clinical examination forms and were linked to the clinical dataset only after completion of all follow-up measurements.

Before study initiation, examiner calibration was performed in 10 volunteers who were not included in the study. Probing pocket depth and clinical attachment level measurements were repeated at six sites per tooth, and intra-examiner reproducibility was assessed. The calibrated examiner demonstrated high reproducibility, with a κ value of 0.896, and repeated measurements differed by no more than 1 mm at 90% of sites.

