2.5. Statistical analysis

All statistical analyses were performed using IBM SPSS Statistics version 30.0 (IBM Corp., Armonk, NY, USA). Continuous variables were expressed as mean \pm standard deviation or median [interquartile range], as appropriate, and categorical variables as number and percentage. Baseline comparisons between probiotic product users and non-users were performed using the independent-samples t test or Mann-Whitney U test for continuous variables and the chi-square test or Fisher's exact test for categorical variables.

Clinical outcomes and OHIP-14 total scores at 1 and 3 months were analyzed using regression models adjusted for age, sex, current smoking status, education level, previous periodontal treatment and the baseline value of the corresponding outcome. Current smoking was coded as current smoking versus non-current smoking. Continuous outcomes, including PI, mean PPD, CAL, BOP and OHIP-14 total score, were analyzed using linear regression

models. Count outcomes, including the number of sites with PPD ≥ 5 mm, were analyzed using generalized linear models with a log link and expressed as rate ratios with 95% confidence intervals. Additional sensitivity models included previous probiotic recommendation and prior familiarity with the term “probiotic”.

Within-group changes in clinical and OHRQoL outcomes across baseline, 1 month and 3 months were analyzed using the Friedman test. Questionnaire-based probiotic knowledge/familiarity, attitude, acceptance, preference, satisfaction and adherence-related variables were analyzed according to item type using the chi-square test, Fisher’s exact test, Mann–Whitney U test or Wilcoxon signed-rank test, as appropriate. Factors associated with reported probiotic product use were evaluated using multivariable logistic regression. A two-sided p value <0.05 was considered statistically significant.

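### The user/non-user label spans the whole follow-up but is also the exposure in the 1-month models, so product use begun after the 1-month visit can count as exposure for it

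*Combined protocol and SAP*

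**What the plan says.** Section 2.2 defines exposure once per patient: "Group classification was based on self-reported use of probiotic supplements or commercially labelled probiotic products during active periodontal treatment and post-treatment follow-up". The comparison group is the complement over the same period: "those reporting no probiotic supplement or commercially labelled probiotic product use during the same interval were classified as non-users". Users face no minimum and no required start: "No probiotic strain, dose, formulation, frequency, duration or adherence protocol was prescribed as part of the study".

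Under section 2.3, clinical measurements "were performed at baseline, 1 month, and 3 months after NSPT by a calibrated examiner". Product-use data were kept apart from the examination forms and "were linked to the clinical dataset only after completion of all follow-up measurements". The section does not say at which visit, or how often, patients were asked about use.

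Under section 2.5, "Clinical outcomes and OHIP-14 total scores at 1 and 3 months were analyzed using regression models adjusted for age, sex, current smoking status, education level", among other covariates that include the baseline value of the outcome. No separate exposure definition is given for the 1-month models. The sensitivity analyses add covariates only: "Additional sensitivity models included previous probiotic recommendation and prior familiarity with the term". The documents describe no start date, visit-specific exposure, landmark rule or analysis of timing.

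**The concern.** The exposure window runs past the first modelled outcome. Month 3 is the last visit described, so post-treatment follow-up is most naturally read as running to month 3. A patient who first used a product in month 2 cannot be a non-user, and no third group or exclusion is described. If that patient is a user, the 1-month model treats as exposed someone who had used nothing when the outcome was measured.

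Two things can follow at 1 month. If starting late is unrelated to healing, late starters dilute any real difference. If it depends on how the mouth is doing at 1 month, the label carries information about the outcome itself and a difference appears with no effect present. Its sign depends on whether patients who heal poorly or well are more likely to start. The 1-month status is not a covariate in any planned model, so the planned adjustment cannot fully remove this.

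**Working it through.** **Inputs from the documents.** Standardized effect 0.50, two-sided alpha 0.05, 80% power, 63 per group required, 65 per group analysed (section 2.1); adjustment for the baseline value of the outcome (section 2.5). The documents give no share of late starters, no start pattern and no correlations. Those are assumed below and only show scale.

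**1. The plan's own figure.** n = 2(1.96 + 0.84)²/0.50² = 62.8, so 63 per group. This reproduces. At 65 per group, power = Φ(0.50/√(2/65) − 1.96) = Φ(2.85 − 1.96) = 81.3% (80.8% by t test).

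**2. Dilution at 1 month.** Let f be the share of users who first used a product after the 1-month visit, unrelated to outcome. The contrast becomes 0.50(1 − f). Power is Φ(d/(√(1 − r²)·√(2/65)) − 1.96), where r is the baseline-to-follow-up correlation (r = 0 means unadjusted).

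| f | d (SD) | power, unadjusted | power, adjusted, r = 0.6 |
|---|---|---|---|
| 0% | 0.50 | 81.3% | 94.6% |
| 10% | 0.45 | 72.8% | 89.4% |
| 20% | 0.40 | 62.6% | 81.3% |
| 30% | 0.35 | 51.4% | 70.3% |

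The unadjusted t test gives 80.8, 72.1, 61.9 and 50.8%. Baseline adjustment restores precision. It does not restore the diluted estimate.

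**3. Outcome-driven starting, no true effect.** Assume 130 patients and 35% early users. Of the rest, 30% start later if their 1-month value is above the median and 10% if it is not. Outcomes are standard normal, with correlation 0.6 between 1 and 3 months.

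- Late starters: 0.65 × 0.20 = 0.13 of all patients. Users: 0.35 + 0.13 = 0.48. So f = 0.13/0.48 = 27%.
- The mean above the median is 0.798 SD. Late starters average 0.798 × (0.30 − 0.10)/0.40 = 0.399 SD. Never-users average 0.798 × (0.70 − 0.90)/1.60 = −0.100 SD.
- Unadjusted 1-month difference: 0.27 × 0.399 + 0.100 = 0.208 SD.
- Covariance of label and 1-month outcome: c = 0.48 × 0.52 × 0.208 = 0.0519.
- Baseline-adjusted coefficient at 1 month: c(1 − r²)/(0.2496 − r²c²). At 3 months: c(0.6 − r·r₃)/(0.2496 − r²c²), where r₃ is the baseline-to-3-month correlation.
- Standard error: √((1 − r²)/(130 × 0.2496)), with r₃ in place of r at 3 months. The false-positive rate is the chance that a normal variable with mean coefficient/SE falls outside ±1.96.

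| r, r₃ | 1 month: bias, false positives | 3 months: bias, false positives |
|---|---|---|
| unadjusted | 0.21 SD, 22% | 0.12 SD, 11% |
| 0.5, 0.5 | 0.16 SD, 18% | 0.07 SD, 8% |
| 0.6, 0.6 | 0.13 SD, 16% | 0.05 SD, 6% |
| 0.7, 0.7 | 0.11 SD, 14% | 0.02 SD, 5% |
| 0.6, 0.36 | 0.13 SD, 16% | 0.08 SD, 8% |

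Simulation of the same set-up (10,000 replicates) agrees with the formula to about 0.001 SD and half a percentage point. It puts the r = 0.7 rate at 1 month at 13%. Swapping the 30% and 10% reverses the sign.

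**4. Power after re-defining 1-month exposure.** If late starters count as non-users at 1 month, the groups are 65(1 − f) and 65(1 + f). Unadjusted power at d = 0.50 is 81.0% for f = 10% (58.5/71.5), 79.8% for 20% (52/78) and 77.6% for 30% (45.5/84.5).

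**The case against.** The strongest reply is that the definition need not mean any use at any time. It can be read as use in both periods, in which case users had started by active treatment and the 1-month order is sound. That reading is open. It leaves a late starter in neither group, however, and the text provides no third category, so the rule still needs correcting.

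A reader might infer that patients did start late, or did so because of their 1-month result. The documents report neither. The case rests on what the rule permits, and every share used above is assumed.

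A reader might also infer that the 3-month comparison is compromised to the same degree. Only unadjusted figures would suggest a sizeable problem there. The plan adjusts for baseline, and with that adjustment the 3-month false-positive rate stays at 5–8%. Month 3 is also the time point on which the sample size rests. Similarly, the fall in power to 51–73% applies to an unadjusted test. With r = 0.6 and 20% late starters, the adjusted model keeps about 81%.

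Blinding of the examiner and separate records protect the measurements but do not order exposure before outcome. The disclaimer of causal inference in section 2.1 is attached to the sample-size calculation. Even a purely associational statement about users at 1 month needs to say who was using by then.

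**Conclusion.** The concern holds for the 1-month models. As written, the rule lets use that began after the 1-month outcome count as exposure for it, and no planned analysis would reveal or correct this. How often it happened is unknown.

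With 10–30% late starters, a 0.50 SD effect shrinks to 0.45–0.35 SD. With outcome-driven starting at 30% versus 10%, no true effect and a baseline correlation of 0.5–0.7, the planned adjustment leaves a spurious difference of about 0.11–0.16 SD and 13–18% false positives, against a nominal 5%. Milder selection would give less. The direction cannot be known from the documents, so a reader cannot discount it.

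At 3 months the same mechanism leaves about 0.02–0.08 SD and 5–8%. That calls for a sensitivity analysis or a stated limitation, and does not by itself undermine the 3-month comparison.

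**What to change.** State whether a user must report use in either period or in both, when use was asked about, and how a patient who first used a product after the 1-month visit was classified.

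Where start timing was recorded or can be recovered:

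- in the 1-month models, define users by use begun before the 1-month visit;
- at 3 months, keep the stated definition as the main analysis and add a sensitivity analysis with exposure fixed at the 1-month visit, with late starters reclassified or shown separately;
- report the number of late starters.

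Where timing cannot be recovered, present the 1-month comparison as descriptive, draw no user versus non-user conclusion from it, and state the limitation for month 3. The text describes a completed sample, so the remedy should not depend on adding questions at visits already held.

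The cost is mainly wording and one extra model per outcome. The user group at 1 month becomes slightly smaller, with little loss of power up to 30% late starters, or the 1-month claim becomes weaker.

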2.3. Clinical assessment

Clinical periodontal measurements including PI, BOP, PPD, CAL were performed at baseline, 1 month, and 3 months after NSPT by a calibrated examiner ([name]) who was not involved in treatment delivery and was blinded to participants' probiotic product-use status and questionnaire responses. Participants were instructed not to disclose their probiotic product use during clinical examinations. Probiotic product-use data and questionnaire responses were recorded separately from the clinical examination forms and were linked to the clinical dataset only after completion of all follow-up measurements.

Before study initiation, examiner calibration was performed in 10 volunteers who were not included in the study. Probing pocket depth and clinical attachment level measurements were repeated at six sites per tooth, and intra-examiner reproducibility was assessed. The calibrated examiner demonstrated high reproducibility, with a κ value of 0.896, and repeated measurements differed by no more than 1 mm at 90% of sites.

2.4. Questionnaire and patient-reported assessment

At baseline, participants completed a structured questionnaire including demographic and health-related information, previous periodontal treatment history, probiotic knowledge/familiarity, attitudes toward probiotic use in periodontal therapy, previous probiotic exposure and probiotic form/source preferences. The questionnaire framework was adapted from previously used probiotic knowledge and consumption surveys and from the approved study protocol (Patait et al., 2022; Sahin, 2026; Wang et al., 2025).

Baseline probiotic knowledge/familiarity was assessed using items related to prior awareness of the term "probiotic", self-rated knowledge level, correct identification of the probiotic definition and perceived general probiotic benefit. These variables were additionally combined into an exploratory baseline knowledge/familiarity index.

Attitudes toward probiotic use in periodontal therapy were assessed using Likert-type items addressing perceived periodontal benefit, willingness to use probiotics as part of periodontal treatment, confidence in probiotic use if recommended by a dentist and ease of acceptance when adequate explanation was provided. A high acceptance profile was defined a priori as agreement or strong agreement with at least three of four predefined attitude items.

The questionnaire also included items on product and formulation preferences, including preferred supplement formulation, commercially labelled probiotic product type and preferred route/form of use. Traditional homemade fermented foods were recorded only as dietary fermented-food habits and were not used to define exposure. These items were used descriptively to characterize patient preferences and were not used to define a standardized probiotic exposure.

OHRQoL was assessed using the Turkish version of the Oral Health Impact Profile-14 (OHIP-14-TR) at baseline, 1 month and 3 months (Mumcu et al., 2006; Slade, 1997). Each item was scored on a 5-point Likert scale, and total scores ranged from 0 to 56, with higher scores indicating poorer OHRQoL. At follow-up, additional patient-reported measures included self-rated current oral health, perceived change in oral problems since treatment, overall treatment satisfaction and future willingness to use probiotics if recommended. Among probiotic product users, probiotic-related experience was also recorded, including satisfaction with probiotic use and self-reported adherence.

2.5. Statistical analysis

All statistical analyses were performed using IBM SPSS Statistics version 30.0 (IBM Corp., Armonk, NY, USA). Continuous variables were expressed as mean \pm standard deviation or median [interquartile range], as appropriate, and categorical variables as number and percentage. Baseline comparisons between probiotic product users and non-users were performed using the independent-samples t test or Mann-Whitney U test for continuous variables and the chi-square test or Fisher's exact test for categorical variables.

Clinical outcomes and OHIP-14 total scores at 1 and 3 months were analyzed using regression models adjusted for age, sex, current smoking status, education level, previous periodontal treatment and the baseline value of the corresponding outcome. Current smoking was coded as current smoking versus non-current smoking. Continuous outcomes, including PI, mean PPD, CAL, BOP and OHIP-14 total score, were analyzed using linear regression

models. Count outcomes, including the number of sites with PPD ≥ 5 mm, were analyzed using generalized linear models with a log link and expressed as rate ratios with 95% confidence intervals. Additional sensitivity models included previous probiotic recommendation and prior familiarity with the term “probiotic”.

Within-group changes in clinical and OHRQoL outcomes across baseline, 1 month and 3 months were analyzed using the Friedman test. Questionnaire-based probiotic knowledge/familiarity, attitude, acceptance, preference, satisfaction and adherence-related variables were analyzed according to item type using the chi-square test, Fisher’s exact test, Mann–Whitney U test or Wilcoxon signed-rank test, as appropriate. Factors associated with reported probiotic product use were evaluated using multivariable logistic regression. A two-sided p value <0.05 was considered statistically significant.

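### Baseline plaque is left out of every outcome model except the plaque model, and the PI, BOP and OHIP-14 models carry no measure of baseline pocket severity

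*Combined protocol and SAP*

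**What the plan says.** Exposure was not assigned. Section 2.2 states: "Group classification was based on self-reported use of probiotic supplements or commercially labelled probiotic products during active periodontal treatment and post-treatment follow-up".

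Section 2.3 states: "Clinical periodontal measurements including PI, BOP, PPD, CAL were performed at baseline, 1 month, and 3 months after NSPT". The examiner was calibrated and blinded to product use, so plaque and pocket measures exist at baseline for the analysed patients.

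Section 2.5 models the 1-month and 3-month outcomes with regressions "adjusted for age, sex, current smoking status, education level, previous periodontal treatment and the baseline value of the corresponding outcome". This set applies to two model types:

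- Linear: "Continuous outcomes, including PI, mean PPD, CAL, BOP and OHIP-14 total score, were analyzed using linear regression".
- Log-link: "Count outcomes, including the number of sites with PPD ≥ 5 mm, were analyzed using generalized linear models with a log link".

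The only extension planned is: "Additional sensitivity models included previous probiotic recommendation and prior familiarity with the term" probiotic. Section 2.5 also plans baseline tests between the groups. No propensity score or other use of baseline clinical variables across outcomes is described.

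**The concern.** In a comparison of people who chose a product with people who did not, an obvious rival explanation is that the choosers also clean better and heal better after debridement for that reason. Age, sex, smoking, education and treatment history capture some of this, but none of them measures oral hygiene. Adjusting for an outcome's own baseline handles where the patient started on that outcome. It does not handle a separate factor that affects the response to treatment.

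Baseline PI was measured blind and bears directly on hygiene, yet it is used only in the PI model. Baseline pocket severity, a prognostic factor rather than a hygiene proxy, is likewise missing from the models for PI, BOP and OHIP-14. The OHIP-14 model contains no clinical baseline measure at all.

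What is at stake is the adjusted difference between users and non-users. If users do have less plaque at baseline, and less plaque goes with better results, the error favours the product.

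**Working it through.** **1. Which baseline clinical measures each model contains (section 2.5)**

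| Outcome model | Baseline PI | Baseline pocket or attachment severity |
|---|---|---|
| PI | yes (own baseline) | no |
| Mean PPD | no | yes (own baseline) |
| CAL | no | yes (own baseline) |
| BOP | no | no |
| Sites with PPD ≥ 5 mm | no | yes (own baseline) |
| OHIP-14 | no | no |

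Plaque is missing from five of the six named outcomes and severity from three. The two sensitivity covariates concern probiotics, so they leave the table unchanged.

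**2. The plan's own figure, used as the yardstick (section 2.1)**

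The inputs are an effect size of 0.50, two-sided α of 0.05 and 80% power. By the normal approximation, n = 2 × ((1.960 + 0.842)/0.50)² = 62.8, so 63 per group, as stated. A t-test calculation gives 63.8, so 64. Power with the 65 per group analysed is 81%.

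**3. Illustrative size of the bias**

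Neither input below is in the document, so both are assumed:

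- raw baseline PI difference between groups: 0.3 to 0.5 SD;
- partial standardized slope of baseline PI on the 3-month outcome: 0.2 to 0.3.

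The bias is the partial slope times the PI imbalance that *remains* after the covariates already in the model. The raw imbalance is the wrong input. Assume that baseline PI correlates r = 0.5 with the outcome's own baseline, and that this baseline differs between groups only through PI. The remaining share is then 1 − r² = 1 − 0.25 = 0.75.

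- Remaining imbalance: 0.75 × 0.3 = 0.225 SD, to 0.75 × 0.5 = 0.375 SD.
- Bias: 0.225 × 0.2 = 0.045 SD, to 0.375 × 0.3 = 0.1125 SD.
- As a share of the 0.50 design effect: 9% to 22.5%.

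**4. Effect on the 5% test if the product does nothing**

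The standard error in SD units is √(2/65) = 0.175. If the outcome's own baseline correlates 0.5 with the outcome (assumed), it is √(0.75 × 2/65) = 0.152. The rejection probability is 1 − Φ(1.96 − bias/SE) + Φ(−1.96 − bias/SE).

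| Bias (SD) | SE 0.175 | SE 0.152 |
|---|---|---|
| 0.045 | 5.8% | 6.0% |
| 0.1125 | 9.8% | 11.5% |

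This illustration is for the linear models. It does not carry over directly to the rate ratio for deep sites.

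**5. Would the planned baseline tests reveal the problem?**

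With 65 per group, a two-sided 5% t test detects a 0.3 SD difference with about 40% power and a 0.5 SD difference with about 81%. A non-significant baseline comparison would not rule out an imbalance of this size.

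**6. Cost of two further covariates**

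Counting education as one term, the present model has 7 terms and 130 − 7 − 1 = 122 residual degrees of freedom. With two more it has 120. If both were uninformative, the standard error would rise by about 0.8% (√(122/120) = 1.008). An imbalance of d SD in one covariate inflates the variance of the exposure term by 1 + d²/4, which is 1.02 at 0.3 SD and 1.06 at 0.5 SD.

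**The case against.** The case for the plan as written has real force.

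- **The models are not bare.** Each carries five covariates besides the outcome's own baseline, and smoking, education and treatment history are partial markers of health behaviour. This stands, and it is why the working uses a remaining imbalance. A reader might multiply the raw imbalance by the slope, obtaining up to 0.15 SD and about 17% false rejection. That calculation ignores what the existing adjustment removes, and the document supplies neither input.
- **Severity is partly handled.** All patients are Stage III Grade B, and the PPD, CAL and deep-site models already contain severity through their own baseline. This stands. A reader might infer that severity is missing throughout, but the gap is confined to PI, BOP and OHIP-14. Restriction by stage and grade narrows severity in those models without equalising it.
- **Baseline PI is an imperfect proxy.** It precedes the oral hygiene instruction given to everyone, so it does not measure cleaning during follow-up. The questionnaire may also hold something better: "participants completed a structured questionnaire including demographic and health-related information, previous periodontal treatment history, probiotic knowledge/familiarity" does not itemise the health-related part. This limits how much confounding the fix removes. It does not justify leaving out the one hygiene-related measure that is named.
- **Causal inference is disclaimed.** Section 2.1 does so when explaining the sample size. That softens the consequence, but adjusted comparisons are still planned and will be read as such.

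A reader might also take the homemade fermented foods, which "were recorded as dietary fermented-food habits when reported but were not used to define probiotic exposure", to have been asked about in only some patients, and so to be a further uncontrolled confounder. The document does not show this. Section 2.4 describes the recording alongside a structured questionnaire that participants completed, and the phrase may simply mean that positive answers were noted. It forms no part of this point.

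**Conclusion.** The gap is established by the text: baseline plaque is absent from five of six outcome models and baseline severity from three, although both were measured. How much bias results cannot be established. Under the stated assumptions (remaining PI imbalance about 0.22 to 0.38 SD, partial slope 0.2 to 0.3) it is about 0.045 to 0.11 SD, and the 5% test rejects about 6 to 11% of the time. That is modest beside the 0.50 SD used for planning, and it would be nil if the groups happen to have equal plaque given the other covariates.

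The document does not support a claim that the main comparison is invalid, or that a bias is known to exist. It supports a narrower conclusion: an inexpensive adjustment for a plausible confounder is missing and should be made.

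**What to change.** In section 2.5:

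1. Add baseline PI to the mean PPD, CAL, BOP, deep-site and OHIP-14 models.
2. Add baseline mean PPD to the PI, BOP and OHIP-14 models. It is not needed in the mean PPD, CAL and deep-site models, where the outcome's own baseline already supplies severity and a second such measure would be redundant or probably collinear.
3. Do not adjust for follow-up PI, which may lie on the path from product use to outcome.
4. Report these results beside those from the models now in section 2.5, and disclose that the covariates were added to the plan and when. Section 2.1 already describes follow-up as complete.

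The cost is revised SAP wording and one or two degrees of freedom per model with 130 patients. No new data are needed and the sample size does not change. The covariates may improve precision if they are prognostic. The report should also say that baseline PI predates the hygiene instruction, so some confounding by hygiene during follow-up may remain.
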